#### **7.2.2 IRB Requirements for PI Reporting at Continuing Review**

Please refer to the reporting requirements in Policy 801: Reporting Research Events found [here](#).

### **7.3 NCI CLINICAL DIRECTOR REPORTING**

Problems expeditiously reported to the OHSRP in iRIS will also be reported to the NCI Clinical Director. A separate submission is not necessary as reports in iRIS will be available to the Clinical Director.

In addition to those reports, all deaths that occur within 30 days after receiving a research intervention should be reported via email to the Clinical Director unless they are due to progressive disease.

To report these deaths, please send an email describing the circumstances of the death to [name] at [[contact]](mailto:[contact]) within one business day of learning of the death.

### **7.4 NIH REQUIRED DATA AND SAFETY MONITORING PLAN**

#### **7.4.1 Principal Investigator/Research Team**

The clinical research team will meet on a weekly basis when patients are being actively treated on the trial to discuss each patient. Decisions about dose level enrollment and dose escalation if applicable will be made based on the toxicity data from prior patients.

All data will be collected in a timely manner and reviewed by the principal investigator or a lead associate investigator. Events meeting requirements for expedited reporting as described in section **7.2.1** will be submitted within the appropriate timelines.

The principal investigator will review adverse event and response data on each patient to ensure safety and data accuracy. The principal investigator will personally conduct or supervise the investigation and provide appropriate delegation of responsibilities to other members of the research staff.

## **8 SPONSOR PROTOCOL/SAFETY REPORTING**

### **8.1 DEFINITIONS**

#### **8.1.1 Adverse Event**

Any untoward medical occurrence in a patient or clinical investigation subject administered a pharmaceutical product and which does not necessarily have a causal relationship with this

treatment. An adverse event (AE) can therefore be any unfavorable and unintended sign (including an abnormal laboratory finding), symptom, or disease temporally associated with the use of a medicinal (investigational) product, whether or not related to the medicinal (investigational) product (ICH E6 (R2))

#### 8.1.2 Serious Adverse Event (SAE)

An adverse event or suspected adverse reaction is considered serious if in the view of the investigator or the sponsor, it results in any of the following:

- Death,
- A life-threatening adverse event (see section [8.1.3](#))
- Inpatient hospitalization or prolongation of existing hospitalization
  - A hospitalization/admission that is pre-planned (i.e., elective or scheduled surgery arranged prior to the start of the study), a planned hospitalization for pre-existing condition, or a procedure required by the protocol, without a serious deterioration in health, is not considered a serious adverse event.
  - A hospitalization/admission that is solely driven by non-medical reasons (e.g., hospitalization for patient or subject convenience) is not considered a serious adverse event.
  - Emergency room visits or stays in observation units that do not result in admission to the hospital would not be considered a serious adverse event. The reason for seeking medical care should be evaluated for meeting one of the other serious criteria
- Persistent or significant incapacity or substantial disruption of the ability to conduct normal life functions
- A congenital anomaly/birth defect.
- Important medical events that may not result in death, be life-threatening, or require hospitalization may be considered a serious adverse drug experience when, based upon appropriate medical judgment, they may jeopardize the patient or subject and may require medical or surgical intervention to prevent one of the outcomes listed in this definition.

#### 8.1.3 Life-threatening

An adverse event or suspected adverse reaction is considered "life-threatening" if, in the view of either the investigator or sponsor, its occurrence places the patient or subject at immediate risk of death. It does not include an adverse event or suspected adverse reaction that, had it occurred in a more severe form, might have caused death. (21CFR312.32)

#### 8.1.4 Severity

The severity of each Adverse Event will be assessed utilizing the CTCAE version 4.0.

#### 8.1.5 Relationship to Study Product

All AEs will have their relationship to study product assessed using the terms: related or not related.

- Related – There is a reasonable possibility that the study product caused the adverse event. Reasonable possibility means that there is evidence to suggest a causal relationship between the study product and the adverse event.
- Not Related – There is not a reasonable possibility that the administration of the study product caused the event.

#### 8.1.6 Adverse Events of Special Interest (AESI)

See Section **3.4.2**.

### **8.2 ASSESSMENT OF SAFETY EVENTS**

AE information collected will include event description, date of onset, assessment of severity and relationship to study product and alternate etiology (if not related to study product), date of resolution of the event, seriousness and outcome. The assessment of severity and relationship to the study product will be done only by those with the training and authority to make a diagnosis and listed on the Form FDA 1572 as the site principal investigator or sub-investigator. AEs occurring during the collection and reporting period will be documented appropriately regardless of relationship. AEs will be followed through resolution.

SAEs will be:

- Assessed for severity and relationship to study product and alternate etiology (if not related to study product) by a licensed study physician listed on the Form FDA 1572 as the site principal investigator or sub-investigator.
- Recorded on the appropriate SAE report form, the medical record and captured in the clinical database.
- Followed through resolution by a licensed study physician listed on the Form FDA 1572 as the site principal investigator or sub-investigator.

For timeframe of recording adverse events, please refer to section **6.1**. All serious adverse events recorded from the time of first investigational product administration must be reported to the sponsor with the exception of any listed in section **8.4**.

### **8.3 REPORTING OF SERIOUS ADVERSE EVENTS**

Any AE that meets protocol-defined serious criteria or meets the definition of Adverse Event of Special Interest that require expedited reporting must be submitted immediately (within 24 hours of awareness) to OSRO Safety using the CCR SAE report form.

All SAE reporting must include the elements described in section **8.2**.

SAE reports will be submitted to the Center for Cancer Research (CCR) at: [[contact]](mailto:[contact]) and to the CCR PI and study coordinator. CCR SAE report form and instructions can be found at: <https://ccrod.cancer.gov/confluence/display/CCRCRO/Forms+and+Instructions>

Following the assessment of the SAE by OSRO, other supporting documentation of the event may be requested by the OSRO Safety and should be provided as soon as possible.

#### **8.4 WAIVER OF EXPEDITED REPORTING TO CCR**

As death due to disease progression is part of the study objectives (OS) and captured as an endpoint in this study, death due to disease progression will not be reported in expedited manner to the Sponsor. However, if there is evidence suggesting a causal relationship between the study drug and the event, report the event in an expedited manner according to section **8.3**.

Hospitalization that is deemed to be due to disease progression, and not attributable to the intervention will not be reported as an SAE. The event, and the assessment that it was caused by disease progression will be documented in the medical records. The causality assessment of hospitalization will be re-evaluated any time when new information is received. If the causality assessment changes from disease progression to related to the study intervention, SAE report will be sent to the Sponsor in an expedited manner according to section **8.3**. If there is any uncertainty whether the intervention is a contributing factor to the event, the event should be reported as AE or SAE as appropriate.

#### **8.5 REPORTING CRITERIA TO THE PHARMACEUTICAL COLLABORATORS**

All events listed below must be reported in the defined timelines to [[contact]](mailto:[contact]).

The CCR Office of Regulatory Affairs will send all reports to the manufacturer as described below.

##### **8.5.1 Expedited Adverse Event Reporting Criteria to the IND Manufacturer**

All safety reports and annual reports that are submitted to the FDA will be submitted to AstraZeneca.

A copy of the MedWatch report or equivalent form must be faxed to AstraZeneca at the time the event is reported to the FDA.

A cover page should accompany the MedWatch form or equivalent form indicating the following:

- “Notification from an Investigator Sponsored Study”
- The investigator IND number assigned by the FDA
- The investigator’s name and address
- The trial name/title and AstraZeneca ISS reference number (ESR-16-11932)

\* Sponsor must also indicate, either in the SAE report or the cover page, the causality of events in relation to all study medications and if the SAE is related to disease progression, as determined by the principal investigator.

\* Send SAE report and accompanying cover page by way of email to AstraZeneca’s designated mailbox: [[contact]](mailto:[contact])

All SAEs will be reported, whether or not considered causally related to the investigational product, or to the study procedure(s). The reporting period for SAEs is the period immediately following the time that written informed consent is obtained through 90 days after the last dose of durvalumab + tremelimumab or until the initiation of alternative anticancer therapy. The investigator and/or Sponsor are responsible for informing the Ethics Committee and/or the Regulatory Authority of the SAE as per local requirements.

If a non-serious AE becomes serious, this and other relevant follow-up information must also be provided to AstraZeneca.

Serious adverse events that do not require expedited reporting to the FDA still need to be reported to AstraZeneca preferably using the MedDRA coding language for serious adverse events. This information should be reported on a monthly basis and under no circumstance less frequently than quarterly.

The sponsor must inform the FDA, via a MedWatch form or equivalent form, of any serious or unexpected adverse events that occur in accordance with the reporting obligations of 21 CFR 312.32, and will concurrently forward all such reports to AstraZeneca. A copy of the MedWatch/AdeERs report or equivalent form must be faxed to AstraZeneca at the time the event is reported to the FDA. It is the responsibility of the sponsor to compile all necessary information and ensure that the FDA receives a report according to the FDA reporting requirement timelines and to ensure that these reports are also submitted to AstraZeneca at the same time.

## 8.5.2 Other events requiring reporting

### 8.5.2.1 Overdose

Any overdose of a study subject with durvalumab + tremelimumab, with or without associated AEs/SAEs, is required to be reported within 24 hours of knowledge of the event to the sponsor and AstraZeneca/MedImmune Patient Safety or designee using the designated Safety e-mailbox (see Section 8.5.1 for contact information). If the overdose results in an AE, the AE must also be recorded as an AE (see Section 16.5). Overdose does not automatically make an AE serious, but if the consequences of the overdose are serious, for example death or hospitalization, the event is serious and must be recorded and reported as an SAE (see Section 16.5). There is currently no specific treatment in the event of an overdose of durvalumab or tremelimumab.

### 8.5.2.2 Hepatic function abnormality

Hepatic function abnormality (as defined in Section 3.4.2.) in a study subject, with or without associated clinical manifestations, is required to be reported as “hepatic function abnormal” ***within 24 hours of knowledge of the event*** to the sponsor and AstraZeneca/MedImmune Patient Safety using the designated Safety e-mailbox (see Section 7.4 for contact information), unless a definitive underlying diagnosis for the abnormality (e.g., cholelithiasis or bile duct obstruction) that is unrelated to investigational product has been confirmed.

- If the definitive underlying diagnosis for the abnormality has been established and is unrelated to investigational product, the decision to continue dosing of the study subject will be based on the clinical judgment of the investigator.
- If no definitive underlying diagnosis for the abnormality is established, dosing of the study subject must be interrupted immediately. Follow-up investigations and inquiries must be initiated by the investigational site without delay.

Each reported event of hepatic function abnormality will be followed by the investigator and evaluated by the sponsor and AstraZeneca/MedImmune.

## **8.6 REPORTING PREGNANCY**

All required pregnancy reports/follow-up to OSRO will be submitted to: [[contact]](mailto:[contact]) and to the CCR PI and study coordinator. Forms and instructions can be found here:

<https://ccrod.cancer.gov/confluence/display/CCRCRO/Forms+and+Instructions>

### **8.6.1 Maternal exposure**

If a patient becomes pregnant during the course of the study, the study treatment should be discontinued immediately, and the pregnancy reported to the Sponsor no later than 24 hours of when the Investigator becomes aware of it. The Investigator should notify the Sponsor no later than 24 hours of when the outcome of the Pregnancy become known,

Pregnancy itself is not regarded as an SAE. However, congenital abnormalities or birth defects and spontaneous miscarriages that meet serious criteria (see section **8.1.2**) should be reported as SAEs.

The outcome of all pregnancies (spontaneous miscarriage, elective termination, ectopic pregnancy, normal birth, or congenital abnormality) should be followed up and documented.

### **8.6.2 Paternal exposure**

Male patients should refrain from fathering a child or donating sperm during the study and for 180 days after the last dose of durvalumab+ tremelimumab combined therapy or 90 days after the last dose of durvalumab monotherapy, whichever is the longer time period.

Pregnancy of the patient's partner is not considered to be an AE. However, the outcome of all pregnancies (spontaneous miscarriage, elective termination, ectopic pregnancy, normal birth, or congenital abnormality) occurring from the date of the first dose until 180 days after the last dose of durvalumab+ tremelimumab combined therapy or 90 days after the last dose of durvalumab monotherapy, whichever is the longer time period after the last dose should, if possible, be followed up and documented.

## **8.7 REGULATORY REPORTING FOR STUDIES CONDUCTED UNDER CCR-SPONSORED IND**

Following notification from the investigator, CCR, the IND sponsor, will report any suspected adverse reaction that is both serious and unexpected. CCR will report an AE as a suspected adverse reaction only if there is evidence to suggest a causal relationship between the study product and the adverse event. CCR will notify FDA and all participating investigators (i.e., all investigators to whom the sponsor is providing drug under its INDs or under any investigator's IND) in an IND safety report of potential serious risks from clinical trials or any other source, as soon as possible, in accordance to 21 CFR Part 312.32.

All serious events will be reported to the FDA at least annually in a summary format.

## **9 CLINICAL MONITORING**

As a sponsor for clinical trials, FDA regulations require the CCR to maintain a monitoring program. The CCR's program allows for confirmation of: study data, specifically data that could affect the interpretation of primary and secondary study endpoints; adherence to the protocol,

regulations, ICH E6, and SOPs; and human subjects protection. This is done through independent verification of study data with source documentation focusing on:

- Informed consent process
- Eligibility confirmation
- Drug administration and accountability
- Adverse events monitoring
- Response assessment.

The monitoring program also extends to multi-site research when the CCR is the coordinating center.

This trial will be monitored by personnel employed by a CCR contractor. Monitors are qualified by training and experience to monitor the progress of clinical trials. Personnel monitoring this study will not be affiliated in any way with the trial conduct.

## **10 STATISTICAL CONSIDERATIONS**

The primary objective of this pilot trial is to preliminarily evaluate the efficacy of combining tremelimumab and durvalumab in patients with advanced HCC, either alone or with cryoablation, TACE, or RFA, and in patients with advanced biliary tract carcinoma (BTC), either alone or with cryoablation, or RFA.

Cohorts A1 and A2 will enroll patients with advanced HCC, BCLC stage B/C and cohort B will enroll patients with intra/extra-hepatic cholangiocarcinoma. Cohort A1 will have 1 treatment Arm 1 (one without any ablative procedure) and Cohort A2 will have 3 separate treatment arms of 10 patients apiece (one a piece with TACE, RFA, or cryoablation). Cohort B will have 3 separate treatment arms of 10 patients apiece (one without any ablative procedure, one with RFA, and one with cryoablation). The initial 10 patients in cohorts A1 and B, the treatment arms without ablative procedure, must have satisfactory safety and feasibility outcomes in order to permit the treatment arms with ablation to open. This will likely mean that 7 or more of 10 are able to result in complete treatment for the patients. For this pilot, the assignment to specific method of ablation will be done by the multidisciplinary tumor board and thus will not be done randomly. As such, the results must be treated as preliminary and exploratory, requiring independent confirmation of any potentially positive findings.

As each of these 7 treatment arms of 10 patients will be considered a small pilot, each will have same statistical objective, and each of these arms will be evaluated for efficacy as follows. For both HCC and BTC there is no standard second-line therapy in the advanced setting. Based on historical data of investigational agents for both these diseases and stage (i.e. post-sorafenib HCC and post-gem/cis BTC) the 6-month PFS would be not greater than 10-15%[\[42, 43\]](#). In each treatment arm of 10 patients in cohorts A1, A2 and B, the trial will have 82% power to rule out 15% as the proportion stable at 6 month in favor of 50% being stable at 6 months, with each evaluation assuming that a one-sided 0.10 significance level exact binomial test would be performed. If there are 3 patients in 10 who are able to have stable disease at a 6 month evaluation, then the lower one-sided 90% confidence bound for 3/10 is 11.6% (the two sided 80% confidence interval extends from 11.6% to 55.2%). Similarly, with 4 in 10 with stable disease at 6 months, the lower one-sided 90% confidence bound for 4/10 is 18.8% (the two sided

80% confidence interval extends from 18.8% to 64.6%). Thus, in Cohorts A1, A2 or B, 3 or 4 patients out of 10 attaining stable disease at 6 months in any of the 7 treatment arms would tentatively rule out 10-15% as the fraction who would do so, with 90% one sided confidence. The results from the ablation treatment arms of cohort A2 (using TACE, RFA, or cryoablation) may also have their results combined in an exploratory fashion to report their overall efficacy. Similarly, the results from the ablation treatment arms of cohort B (using RFA or cryoablation) may also have their results combined in an exploratory fashion to report their overall efficacy.

Should positive findings be identified in any of the treatment arm of cohorts A1, A2 or cohort B, then after this pilot phase has been concluded, subsequent, more definitive evaluation may be conducted in the appropriate sub-cohorts using larger numbers of patients, as defined by amendments (or separate protocols if warranted) used to describe the expansion cohorts.

It is expected that up to 2 patients per month may be able to enroll onto this trial. Cohort A1 will require 10 evaluable patients, Cohort A2 may require up to 30 evaluable patients and cohort B may require up to 30 evaluable patients. The accrual ceiling for the protocol will be set at 90 patients to allow for a small number of inevaluable patients to be enrolled. Thus, it is expected that 24-36 months may be needed to accrue all patients onto this trial.

To address safety and feasibility of combining tremelimumab and durvalumab in (Cohorts A1 and A2) patients with advanced HCC (either alone or with cryoablation, TACE or RFA) and (Cohort B) in patients with advanced biliary tract carcinoma (BTC) (either alone or with cryoablation or RFA), adverse events will be tabulated by grade per CTCAE 4 and analyzed and reported descriptively.

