## **1. INTRODUCTION**

### **1.1 STUDY OBJECTIVES**

#### 1.1.1 Primary Objective:

- To preliminarily evaluate the 6-month progression free survival (PFS) of combining tremelimumab and durvalumab in patients with advanced HCC (either alone or with cryoablation, TACE or RFA) and in patients with advanced biliary tract carcinoma (BTC) (either alone or with cryoablation or RFA).

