### 6.3.1 Definitions

Evaluable for toxicity: All patients will be evaluable for toxicity from the time of their first treatment with tremelimumab and durvalumab.

Evaluable for objective response: Only those patients who have measurable disease present at baseline, have received at least one cycle of therapy, and have had their disease re-evaluated will be considered evaluable for response. These patients will have their response classified according to the definitions stated below. (Note: Patients who exhibit objective disease progression prior to the end of cycle 1 will also be considered evaluable.)

Evaluable Non-Target Disease Response: Patients who have lesions present at baseline that are evaluable but do not meet the definitions of measurable disease, have received at least one cycle of therapy, and have had their disease re-evaluated will be considered evaluable for non-target disease. The response assessment is based on the presence, absence, or unequivocal progression of the lesions.

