#### 6.3.4 Response Criteria

##### 6.3.4.1 Evaluation of Target Lesions

Complete Response (CR): Disappearance of all target lesions. Any pathological lymph nodes (whether target or non-target) must have reduction in short axis to <10 mm.

Partial Response (PR): At least a 30% decrease in the sum of the diameters of target lesions, taking as reference the baseline sum of diameters.

Progressive Disease (PD): At least a 20% increase in the sum of the diameters of target lesions, taking as reference the smallest sum on study (this includes the baseline sum if that is the smallest on study). In addition to the relative increase of 20%, the sum must also demonstrate an absolute increase of at least 5 mm. (Note: the appearance of one or more new lesions is also considered progressions).

Stable Disease (SD): Neither sufficient shrinkage to qualify for PR nor sufficient increase to qualify for PD, taking as reference the smallest sum of diameters while on study.

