**For Patients with Non-Measurable Disease (i.e., Non-Target Disease)**

Non-Target Lesions	New Lesions	Overall Response
CR	No	CR
Non-CR/non-PD	No	Non-CR/non-PD*

Not all evaluated	No	not evaluated
Unequivocal PD	Yes or No	PD
Any	Yes	PD
* 'Non-CR/non-PD' is preferred over 'stable disease' for non-target disease since SD is increasingly used as an endpoint for assessment of efficacy in some trials so to assign this category when no lesions can be measured is not advised		

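### Section 10 counts stable disease at 6 months, while the primary objective and the 10-15% benchmark are 6-month PFS; the counted event should be defined as progression-free

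*Combined protocol and SAP*

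**What the plan says.** Section 1.1.1 of the protocol gives the primary objective as 6-month PFS: "To preliminarily evaluate the 6-month progression free survival (PFS) of combining tremelimumab and durvalumab in patients with advanced HCC". The Précis says the same.

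Section 10, Statistical Considerations, takes its benchmark from the same endpoint: historically, "the 6-month PFS would be not greater than 10-15" per cent. The counted event then changes name within the paragraph:

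- The power statement is a test to "rule out 15% as the proportion stable at 6 month in favor of 50% being stable at 6 months".
- The first confidence-bound example begins "If there are 3 patients in 10 who are able to have stable disease at a 6 month evaluation", and the 4/10 example follows the same pattern.
- The conclusion rests on "3 or 4 patients out of 10 attaining stable disease at 6 months in any of the 7 treatment arms", which is said to tentatively exclude 10-15%.

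Stable disease is a defined category in this protocol. Section 6.3.4.1 defines it as "Neither sufficient shrinkage to qualify for PR nor sufficient increase to qualify for PD", and the best-overall-response table in Section 6.3.4.3 lists CR, PR and SD as separate outcomes. For patients without measurable lesions the corresponding category is non-CR/non-PD, and the footnote says of stable disease "so to assign this category when no lesions can be measured is not advised". Such patients are foreseen: Section 6.3.1 has a class for "Patients who have lesions present at baseline that are evaluable but do not meet the definitions of measurable disease", and inclusion criterion 2.1.1.4 asks only that disease be evaluable.

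**The concern.** PFS at 6 months counts everyone alive without progression: complete responders, partial responders, patients with stable disease, and patients with non-measurable disease that has not progressed. A count of stable disease, in the sense of Section 6.3.4.1, takes in only one of these groups. No section says that *stable* in Section 10 includes responders or means progression-free.

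Two things would follow from applying the literal wording. A patient in response at 6 months would be a failure, so an arm would score worse for producing responses. And the count would be set against a 10-15% figure that belongs to a different quantity. With 10 patients per arm, moving one or two patients between categories is enough to change what an arm appears to show.

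**Working it through.** **Inputs (Section 10).** n = 10 per arm; null 15%; alternative 50%; exact binomial test, one-sided 0.10; stated power 82%; stated one-sided 90% lower bounds 11.6% (3/10) and 18.8% (4/10).

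**Formulas.** For a cut-off c and success probability p, P(X ≥ c) = Σ C(10,x) p^x (1−p)^(10−x), summed over x = c to 10. The one-sided 90% lower bound L for x successes solves P(X ≥ x | L) = 0.10 (Clopper-Pearson).

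**Step 1: reproduce the plan.** Count every progression-free patient as a success.

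- At p = 0.15 the probabilities of 0, 1, 2 and 3 successes are 0.1969, 0.3474, 0.2759 and 0.1298. Hence P(X ≥ 3) = 0.180 and P(X ≥ 4) = 0.050, so 4 is the smallest cut-off with type I error at or below 0.10.
- At p = 0.50, P(X ≥ 4) = 1 − (1 + 10 + 45 + 120)/1024 = 848/1024 = 0.828, which agrees with the stated 82%.
- Lower bounds: 3/10 gives 0.116 and 4/10 gives 0.188, as stated.

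**Step 2: one arm scored both ways.** Suppose 4 of 10 patients are progression-free at 6 months.

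| Of the 4, in PR | Count as PFS | Literal SD count | Lower bound, literal count | One-sided p against 15%, literal count |
|---|---|---|---|---|
| 0 | 4/10 | 4/10 | 18.8% | 0.050 |
| 1 | 4/10 | 3/10 | 11.6% | 0.180 |
| 2 | 4/10 | 2/10 | 5.5% | 0.456 |

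With one responder the literal count still reaches the lower end of the plan's 3-or-4 statement. With two it reaches neither 3 nor 4, although 6-month PFS in the arm is the same in every row.

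**Step 3: illustration of power on an SD-only count.** Assume that true 6-month PFS is 50% and that a share r of all patients is in response at 6 months. The SD-only success probability is then 0.50 − r. The documents give no value of r for this regimen, so the values below are assumptions.

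| r (assumed) | SD-only probability | P(X ≥ 4) | P(X ≥ 3) |
|---|---|---|---|
| 0% | 0.50 | 0.828 | 0.945 |
| 5% | 0.45 | 0.734 | 0.900 |
| 10% | 0.40 | 0.618 | 0.833 |
| 20% | 0.30 | 0.350 | 0.617 |

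The documents do not tell us how many enrolled patients would have only non-measurable disease, so no figure is attached to that group.

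**The case against.** The strongest reply is that Section 10 fixes its own meaning. The 10-15% enters as a PFS rate, 15% becomes the null in the next step, and the conclusion returns to 10-15%. With PFS as the stated objective, *stable* can sensibly mean only *not progressed*, and no one would knowingly score a complete responder as a failure in a PFS trial. As an account of intent this stands, and the figures bear it out. It does not supply the missing definition: Section 10 is where the counted event is stated, and it uses a term that Section 6.3 defines more narrowly. Section 6.3.5.2 runs stable disease until progression but does not place responders in it.

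Section 1.2.10 reports partial responses and prolonged stability as separate groups. That concerns an earlier study and cannot define terms here; it shows only that the narrower usage occurs in the same document.

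Three stronger readings are tempting, and the documents support none of them.

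- *The 82% power is wrong.* It is not. Read as PFS throughout, it reproduces. Read as stable disease throughout, 15% against 50%, it is also 82.8%; what fails then is the link to the PFS benchmark.
- *The trial has lost power to 73%, 62% or 35%.* Those figures combine an SD-only count with a 50% PFS alternative and assumed response shares. They show what a literal application could cost, not a defect in the stated calculation.
- *Arms with responders would be barred from expansion.* Section 10 says that further evaluation may follow positive findings, through amendments or separate protocols. It does not define positive findings by this count, and it calls the results preliminary and exploratory.

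**Conclusion.** The mismatch is in the text and should be corrected, but it is a fault in how the counted event is named, not in the sample size or the arithmetic. On the likely intent, progression-free at 6 months, all of the stated figures hold. On the literal wording, responders at 6 months count as failures and the result cannot be compared with the PFS benchmark; two partial responders among four progression-free patients turn 4/10 into 2/10. The power losses in the working depend on assumed response shares of 5% to 20% and a true 6-month PFS of 50%, and are illustrative only. Because the trial is a pilot with no binding rule attached to the count, the consequence is a risk of misreporting the primary endpoint rather than of a forced wrong decision.

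**What to change.** In Section 10, replace *stable* and *stable disease* throughout the power statement, the 3/10 and 4/10 examples and the concluding sentence with: alive and without RECIST 1.1 progression at 6 months (CR, PR, SD or non-CR/non-PD). State that death or progression by 6 months counts as failure. RECIST 1.1 is already the standard for response and progression in Section 6.3; naming it also keeps this count separate from the modified irRC that Section 6.4 adds.

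The cost is a wording amendment to one section. It adds no scans and no patients, and N, the 15% null, the 82% power and both intervals stay as they are. The new wording does not settle how a missed 6-month scan is counted; the same amendment could add a sentence on that.

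### Section 10 says 3 or 4 of 10 would rule out 10-15% with 90% one-sided confidence, but 3 of 10 does not rule out 15%; the stated test needs 4 of 10

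*Combined protocol and SAP*

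**What the plan says.** All the relevant statements are in section 10 (Statistical Considerations).

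- **Arms:** "As each of these 7 treatment arms of 10 patients will be considered a small pilot", and all share the same statistical objective.
- **Historical benchmark:** "the 6-month PFS would be not greater than 10-15" per cent.
- **Test:** for each arm, "the trial will have 82% power to rule out 15% as the proportion stable at 6 month in favor of 50% being stable". This refers to an exact binomial test at a one-sided 0.10 level. No rejection count is printed.
- **Bounds:** "the lower one-sided 90% confidence bound for 3/10 is 11.6" per cent (80% interval 11.6% to 55.2%), and "the lower one-sided 90% confidence bound for 4/10 is 18.8" per cent (80% interval 18.8% to 64.6%).
- **Conclusion drawn from these:** "3 or 4 patients out of 10 attaining stable disease at 6 months in any of the 7 treatment arms would tentatively rule out" the whole historical range, and the one-sided confidence claimed for this is 90%.

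The section also says that "the results must be treated as preliminary and exploratory, requiring independent confirmation of any potentially positive findings". It allows positive findings in any arm to lead to a larger evaluation after the pilot, but gives no number that defines a positive finding.

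**The concern.** The concluding sentence attaches one range (10-15%) and one confidence level (90%) to both counts. A result excludes a rate at 90% one-sided confidence only if its lower 90% bound lies above that rate. The bound printed for 3/10 is 11.6%, which is above 10% but below 15%. The conclusion therefore does not follow from the bounds just before it. It also disagrees with the section's own test, whose null value is 15%.

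This is the one place where section 10 turns a count into a reading of the primary endpoint, and it applies to all seven arms. Because no cut-off for a positive finding is given elsewhere, it is also the nearest guide to what would count as one. As worded, an arm with 3 of 10 could be reported as having excluded 15% with 90% confidence when it had failed the planned test.

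**Working it through.** **Inputs, all from section 10:** n = 10 per arm; null rate 15%; target rate 50%; one-sided alpha 0.10, exact binomial; historical range 10-15%; seven arms.

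**1. Reproduce the plan's figures.** For a rule of r or more of 10, the rejection probability at true rate p is P(X ≥ r | p) = 1 − Σ C(10,k) p^k (1−p)^(10−k), summed over k = 0 to r−1.

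- Power at 50% with r = 4: 1 − (1 + 10 + 45 + 120)/1024 = 0.828. This matches the stated 82%.
- Power at 50% with r = 3: 1 − (1 + 10 + 45)/1024 = 0.945. This does not match.
- Exact (Clopper-Pearson) 80% intervals: 11.6% to 55.2% for 3/10 and 18.8% to 64.6% for 4/10. Both match the printed values.

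The printed power therefore belongs to a cut-off of 4 of 10, and the printed bounds are exact limits.

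**2. Find the cut-off of the stated test.** At p = 0.15 the probabilities of 0, 1, 2 and 3 successes are 0.1969, 0.3474, 0.2759 and 0.1298.

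- P(X ≥ 3 | 0.15) = 1 − 0.8202 = 0.180, above 0.10, so 3/10 does not reject.
- P(X ≥ 4 | 0.15) = 1 − 0.9500 = 0.050, below 0.10, so 4/10 rejects.

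**3. Confidence attained** (one minus the exact one-sided p-value).

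| Result | Against 10% | Against 15% |
|---|---|---|
| 3/10 | 1 − 0.0702 = 93.0% | 1 − 0.1798 = 82.0% |
| 4/10 | 1 − 0.0128 = 98.7% | 1 − 0.0500 = 95.0% |

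Only 3/10 against 15% falls short of 90%. This 82.0% confidence and the plan's 82% power are different quantities that happen to be close.

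**4. Would another method rescue the sentence?** For 3/10 against 15%, the mid-p value is 0.115 and the Wald lower bound is 11.4%; neither excludes 15%. The Wilson lower bound, 15.4%, just does. But the plan specifies an exact test, and exact limits reproduce its printed bounds.

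**5. What a 3/10 cut-off would do.** The chance of at least one false signal among m arms is 1 − (1 − a)^m, where a is the per-arm rate from step 3. It assumes independent arms that all have the same true rate.

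| True rate | Arms open | Cut-off 3/10 | Cut-off 4/10 |
|---|---|---|---|
| 15% | 7 | 1 − 0.8202^7 = 75% | 1 − 0.9500^7 = 30% |
| 15% | 2 (no ablation) | 1 − 0.8202^2 = 33% | 1 − 0.9500^2 = 9.7% |
| 10% | 7 | 1 − 0.9298^7 = 40% | 1 − 0.9872^7 = 8.6% |
| 10% | 2 (no ablation) | 1 − 0.9298^2 = 14% | 1 − 0.9872^2 = 2.5% |

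The two-arm rows cover the case where the ablation arms never open, since their opening depends on safety and feasibility in the no-ablation patients.

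**The case against.** The best defence is that no calculation in the section is wrong. The power and both intervals reproduce, and only the summary sentence is loose. It follows directly from the two bounds and lists two counts and two rates in matching order. Read as *respectively* (3/10 rules out 10%, 4/10 rules out 15%), it is correct. The 11.6% bound is on the page, so a careful reader can see that the interval for 3/10 includes 15%. The wording is tentative, the pilot is exploratory, and any expansion is discretionary and would need an amendment or a separate protocol. The false-signal figures describe a rule that the plan never states.

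Much of this stands, and it limits the consequences. The false-signal figures apply only if someone does treat 3/10 as positive against 15%, and the seven-arm figures further require all arms to open. At a true 10%, a 3/10 cut-off has a 7.0% error rate, within the stated 0.10.

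The defence does not make the sentence correct. The paired reading is not in the text: 10-15% is used earlier in the section as a single historical range, and the sentence gives that range and one confidence level to both counts. Tentative or exploratory wording affects how much weight a result carries; it does not turn 82% confidence into 90%.

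**Conclusion.** The point holds. Under the plan's own exact one-sided 0.10 test, an arm needs 4 or more of 10 patients stable at 6 months to rule out 15%. An arm with 3 of 10 rules out 10% but not 15%, and the 90% confidence claimed for it against 15% is in fact 82.0%. These statements rest only on n = 10 and the exact binomial distribution.

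The size of the consequence depends on how the sentence is used. If 3/10 were taken as positive against 15%, the per-arm error rate at a true 15% would rise from 5.0% to 18.0%. The multi-arm figures need the added assumptions of independence and a common true rate. Since the sentence informs expansion without deciding it, this is a modest error. It is still worth correcting, because it misstates how the primary endpoint is to be read.

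**What to change.** Replace the concluding sentence with wording along these lines:

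> In any treatment arm, 4 or more of 10 patients stable at 6 months would tentatively rule out 15% with 90% one-sided confidence and would meet the stated test. A result of 3 of 10 would rule out 10% but not 15%, and would not meet the stated test.

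The cost is one sentence in section 10. The test, sample size, arms and analyses do not change. No multiplicity adjustment is needed for this exploratory pilot. If the authors wish, they could note that with the 4/10 cut-off the chance of at least one false signal is about 30% when all seven arms open, are independent and have a true rate of 15%; the correction does not depend on it.
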